10.3 EFFICACY ANALYSES FOR EUROPEAN MEDICANS AGENCY

The section defines an estimand, termed as “off-treatment hypothetical estimand”, which will be the primary estimand in support of EU filing.

10.3.1 Attributes of Off-treatment Hypothetical Estimand

The attributes of the estimand corresponding to the primary efficacy endpoint are summarized as following:

Treatment Condition of Interest

Participants take assigned treatment by randomization during the double-blind treatment period. In addition, permissible and prohibited medications are described below:

- Participants are allowed to take acute migraine medications (Section 4.4.1 of Protocol) to keep the participants in the study
- Medications with demonstrated efficacy for the prevention of migraine (e.g., amitriptyline, propranolol, topiramate) are prohibited when used for any indication other than migraine prevention
 - Participants taking one medication with demonstrated efficacy for the prevention of migraine may be randomized provided that in the opinion of the investigator:

- Dose has been stable and the medication has been well-tolerated for at least 12 weeks prior to Visit 1, and
- Participant is willing and able to maintain at a stable dose and dosage regimen during the study, which should be assessed to ensure compliance at each study visit
- Enrollment of participants with current use of a migraine prevention medication will be capped at ~15%

Population

The target population is patients suffering from CM satisfying the inclusion and exclusion criteria as specified in Section 4 of the protocol.

The analysis population for off-treatment hypothetical estimand is defined to be all randomized participants who received at least 1 dose of study treatment, had an evaluable baseline period of eDiary data and had at least 1 evaluable post-baseline 4-week period (Weeks 1 to 4, 5 to 8, or 9 to 12) of eDiary data, regardless of whether on study treatment or off study treatment.

On study treatment is from the first dose till the last dose of study intervention. As the analysis-visit mapping window ([Table 16.1-2](#)) is defined for the entire postbaseline period (not limited to the double-blind treatment period for participants who prematurely discontinued), the number of participants in the analysis population for this estimand approach is greater than or equal to the number of participants in the mITT Population for the primary analysis.

Variable

The variable is the same as the primary efficacy endpoint defined in Section [10.2](#), which is the change from baseline in the participant's mean monthly (4-weeks) migraine days across the 12-week treatment period as derived from the eDiary data.

Accounting of Intercurrent Events

Intercurrent events and their handling rules are as follows:

- Participants who started a new migraine prevention treatment after the first dose of double-blind treatment will have their data after starting the new migraine prophylaxis treatment during the follow-up period excluded from the analysis.
- Participants who discontinue study intervention due to all reasons other than starting a new migraine prophylaxis treatment will have their data collected after discontinuation of study intervention, and those off-treatment data will be included in the analysis.

Population-level Summary

The population-level summary for the primary endpoint is the difference in primary variable means between each atogepant group and placebo.

10.3.2 Primary Efficacy Analysis

The primary efficacy endpoint is the change from baseline in mean monthly migraine days across the 12-week treatment period. Baseline is defined as the number of migraine days during the last 28 days prior to the randomization date. The primary efficacy analyses will be based on the Off-treatment Hypothetical Estimand Population.

To obtain the estimate of treatment effect defined in the off-treatment hypothetical estimand, an MMRM similar to the primary analysis specified in Section 10.2.1 will be performed on observed data without imputation before switching to other prophylaxis treatment during the follow up periods. The model terms include treatment group, visit (derived as month), stratification of region, stratification of acute medication overuse, stratification of migraine prevention medication use and number of failures, treatment-by-visit interaction, the baseline monthly migraine days and baseline-by-visit interaction. The analysis will be performed based on all evaluable post-baseline values using only the observed cases without imputation of missing values. Participants are always analyzed based on the treatment group assigned by randomization.

10.3.2.1 Sensitivity Analyses in Missing Data Handling

The sensitivity analyses for missing data handling will be conducted and summarized in this section based on the Off-treatment Hypothetical Estimand Population.

Multiple Imputation

The following multiple imputation sensitivity analysis cannot be completed and has been eliminated from the final SAP due to the low number of participants observed in some of the pattern groups.

If a participant provides less than 14 days of efficacy data during a monthly period regardless on or off study treatment, then he/she is considered to have missing data during that monthly period. When a participant provides at least 14 days of efficacy data during a monthly period, if the number of days with available efficacy data while on study treatment is no less than the one while off study treatment, then he/she is considered to have efficacy data on study treatment during that monthly period; otherwise, he/she is considered to have efficacy data off study treatment during that monthly period.

Missing data are assumed to follow monotone pattern. Any intermediate missing values will be imputed first by the same method discussed in Section 10.2.1.1. Possible monotone missing data patterns are discussed below, and a summary is provided in Table 10.3-1.

Participants may provide three-month efficacy data in the following patterns:

- Three months on study treatment (pattern group 1)
- Two months on study treatment and one month off study treatment (pattern group 2)
- One month on study treatment and two months off study treatment (pattern group 3)
- Three months off study treatment (pattern group 4)

Participants may provide two-month efficacy data in the following patterns:

- Two months on study treatment (pattern group 5)
- One month on study treatment and the other month off study treatment (pattern group 6)
- Two months off study treatment (pattern group 7)

Participants may provide only one-month efficacy data while on or off study treatment (pattern groups 8 and 9, respectively).

The number and percentage of participants in each pattern group will be summarized by treatment group for the estimand analysis population defined in Section 10.3.1.

Table 10.3-1. Monotone Missing Data Patterns

Pattern Group	Month 1	Month 2	Month 3
1	x	x	x
2	x	x	o
3	x	o	o
4	o	o	o
5	x	x	.
6	x	o	.
7	o	o	.
8	x	.	.
9	o	.	.

x = available efficacy data on study treatment;
o = available efficacy data off study treatment;
. = missing data

Participants with missing data up to the 12-week treatment period will have their data imputed using participants in the same treatment group who provide data while off study treatment. Same as before (Section 10.2.1), the imputation of missing data is not based on each of the reasons of early termination, because there may not be sufficient non-missing efficacy data in each of the reason categories to serve as a stable reference.

The details of imputation are as follows:

Step 1. Impute month 2 missing data in pattern groups 8 and 9 by treatment group using data from pattern groups 3, 4, 6, and 7 in the corresponding treatment group based on monotone regression.

Step 2. Impute month 3 missing data in pattern groups 5 - 9 respectively by treatment group using data from pattern groups 2, 3, and 4 in the corresponding treatment group based on monotone regression.

Repeat the above procedures 20 times, then we have 20 complete datasets. The ANCOVA analysis results from these completed datasets are combined for overall estimation and inference using

Rubin's rule (Rubin 1987) to produce a pooled estimate of LS mean difference, its SE, and corresponding p-value for the test of null hypothesis of no treatment effect.

ANCOVA Model Based on 3-month Average of the Monthly Migraine Days

The response variable for the ANCOVA model is the change from baseline in the calculated 3-month average of the monthly migraine days including both on- and off-treatment data during the 12-week treatment period for each participant.

The ANCOVA model includes fixed effects for treatment group, stratification of region, stratification of acute medication use, stratification of migraine prevention medication use and baseline monthly migraine days as a covariate. The treatment difference for atogepant doses versus placebo will be estimated and reported along with the corresponding 95% confidence intervals and nominal p-values for superiority testing. There are no missing data based on this derivation because patients who discontinued the treatment are assumed to maintain the same mean (observed while on treatment) for 3 months (12 weeks).

10.3.3 Secondary Efficacy Analysis

The Secondary efficacy endpoints are listed in the [Table 10.1-1](#). The secondary efficacy analyses will be based on the Off-treatment Hypothetical Estimand Population to support EU filing.

The secondary endpoints for headache days and acute medication use days, , will be analyzed in the same manner as that used to analyze the primary endpoint.

For HIT-6 total score and MSQ v2.1 Role Function-Restrictive domain score, the analysis will be performed similarly to the primary MMRM, with focus on the pairwise contrasts of each dose group to placebo at Week 12. Some participants may have their HIT-6 total score or MSQ v2.1 assessed at Visit 8, which will not be included in MMRM, and instead the summary statistics will be provided.

The secondary endpoint of 50% responders are derived as at least a 50% reduction from baseline in the 3-month average of monthly migraine days based on the observed on- and off-treatment data collected throughout the study before switching to other prophylaxis treatment during the follow-up period. The similar logistic regression model as described in 10.2.2 will be used for analysis.

The population-level summary for this endpoint is the odds ratio from a logistic regression for each atogepant group relative to placebo with baseline monthly migraine days as a covariate, stratification of region, stratification of acute medication overuse, stratification of migraine prevention medication and number of failures, and treatment group as fixed factors.

The graphical approach to control the overall Type I error rate described in Section 10.3.3 (Table 10.3-1 and Figure 10.3-1) will be conducted for primary and secondary efficacy endpoints based on the off-treatment hypothetical estimand analysis population.

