10.2.2 Secondary Efficacy Analysis

The secondary efficacy analyses will be based on the mITT Population to support US filling.

The secondary endpoints for headache days, acute medication use days, performance of daily activities domain score of the AIM-D, and physical impairment domain score of the AIM-D, will be analyzed in the same manner as that used to analyze the primary endpoint.

For MSQ v2.1 Role Function-Restrictive domain score, the analysis will be performed similarly to the primary MMRM, with focus on the pairwise contrasts of each dose group to placebo at Week 12. Some participants may have their MSQ v2.1 assessed at Visit 8, which will not be included in MMRM, and instead the summary statistics will be provided.

The 50% responders, defined as participants with at least a 50% reduction from baseline in the 3-month average of monthly migraine days, will be assessed for each participant. A logistic regression model will be used to analyze the 50% responders across the 12-week treatment period. This model assumes a binary distribution for the response and uses a logit link. The analysis model will include treatment group, stratification of region and stratification of acute medication use, stratification of migraine prevention medication use as categorical fixed effects; baseline value will be included as a covariate. The analysis will be performed based on only the observed cases without imputation of missing values. The treatment difference in terms of odds ratio between each atogepant group and placebo will be estimated and tested from this model. The sample SAS is given as follows

```
proc logistic data = in_data1;
  class trt stratum1 stratum2 stratum3 subjid/param=glm;
  model responder (event = "1")= trt stratum1 stratum2 stratum3 base;
  lsmeans trt / e diff oddsratio cl;
  ods output diffs = oddsratio;
run;
```

Note: Placebo is the reference for “trt”. stratum1, stratum2, and stratum3 are the same with those in primary analysis.

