10.2.3 Analyses for Additional Efficacy Endpoints and Health Outcome Endpoints

For variables with a continuous response range, analyses will be performed similarly to that used for the primary analysis, focusing again on the pairwise contrasts of each dose group to placebo. Baseline in the primary MMRM model will be replaced with corresponding endpoint baseline. There is only one post-baseline assessment for MIDAS and PHQ-9, and thus ANCOVA model will be used to analyze MIDAS and PHQ-9 related endpoints with model terms including treatment group, stratification of region, stratification of acute medication use, stratification of migraine prevention medication use, and corresponding baseline score. For the endpoint change from baseline in each MSQ v2.1 domain score and HIT-6 total score, Week 16 (follow up visit) will not be included in MMRM model fitting.

For variables where the data are essentially binary, comparisons between treatment groups will be done using a generalized linear mixed model for variables with multiple postbaseline assessments. A generalized linear mixed model will assume a binary distribution for the response and uses a logit link. The analysis model will include treatment group, visit, stratification of region, stratification of acute medication overuse, stratification of migraine prevention medication use and number of failures, and treatment group-by-visit interaction as categorical fixed effects; baseline value and baseline-by-visit interaction will be included as covariates. Participants will be included as random effects with unstructured covariance matrix in the model to account for the correlation among repeated measurements. If the model does not converge, then the Toeplitz covariance structure will be used. If the model with the Toeplitz covariance structure does not converge, then the compound symmetry covariance structure will be used. The analysis will be performed based on all postbaseline values using only the observed cases without imputation of missing values. As there is no baseline assessment for the endpoint patient's satisfaction with study medication, baseline monthly migraine days will be included in the model.

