Activity level and activity limitation	
 CFB in monthly activity level at Weeks 1-4, 5-8, and 9-12, and average across the 12-week treatment period; CFB in monthly activity limitation scores at Weeks 1-4, 5-8, and 9-12, and average across the 12-week treatment period 	Weeks 1-4, 5-8, 9-12, and average across the 12-week treatment period	CFB MMRM
HIT-6	
 CFB in total score at Weeks 4, 8, 12, and 16 (week 16 summary only) At least a 5-point improvement (decrease) from baseline in total score at Weeks 4, 8, 12, 16 	Weeks 4, 8, 12, 16	CFB MMRM GLMM
MSQ v2.1	
 CFB in Role Function-Restrictive domain score at Weeks 4, 8, and 16 (week 16 summary only); CFB in Role Function-Preventive domain score at Weeks 4, 8, 12, and 16 (week 16 summary only); CFB in Emotional Function domain score at Weeks 4, 8, 12, and 16 (week 16 summary only). 	Weeks 4, 8, 16	CFB MMRM
Patient Satisfaction with Study Medication (PSSM)	Participants response as “satisfied” or “extremely satisfied” with study medication for migraine prevention at Weeks 4, 8, and 12	Weeks 4, 8, 12	GLMM
MIDAS	
 CFB in total score at Weeks 12 CFB in absenteeism score (questions 1, 3, 5) at Weeks 12 CFB in presenteeism score (questions 2, 4) at Weeks 12 	Weeks 12	ANCOVA
PGIC	Participant assessed as “much better” or “very much better” at Week 12	Weeks 12	Logistic regression model
WPAI: MIGRAINE	CFB in percent work time missed, percent impairment while working, percent overall work impairment, and percent activity impairment due to migraine at Week 12	Week 4, 8, 12	CFB MMRM
PGI-S	CFB (as categorical in levels) in score at Weeks 4, 8, and 12	Weeks 4, 8, 12	MMRM
PHQ-9	CFB in PHQ-9 score at Week 12	Week 12	ANCOVA

Assessment/ Term	Endpoint	Timing	Methodology
EQ-5D-5L	
 CFB in descriptive system index score US-based values at Weeks 1 to 2, at specified windows around Weeks 4, 6, 8, and 12 CFB in descriptive system index score US-based values at Week 16 (follow-up visit) 	Double-blind treatment period	CFB MMRM
		Week 16	Continuous descriptive
	
 CFB in the VAS score at Weeks 1 to 2, at specified windows around Weeks 4, 6, 8, and 12 CFB in the VAS score at Week 16 (follow-up visit) 	Double-blind treatment period	CFB MMRM
		Week 16	Continuous descriptive
PROMIS-PI	CFB in total score at Weeks 4, 8 and 12	Weeks 4, 8, 12	CFB MMRM

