	4 Days after Initial Dose	Treatment Day 5
	5 Days after Initial Dose	Treatment Day 6
	6 Days after Initial Dose	Treatment Day 7

The analysis visit windows for MSQ v2.1 and HIT-6 for mITT Population and Off-treatment Hypothetical Estimand Population are defined as follows:

Table 16.1-5. Efficacy Analysis Visit Definitions for MSQ v2.1 and HIT-6

Analysis Phase	Analysis Visit (Derived)	Scheduled Study Visit (eCRF)	Window
Pretreatment	Baseline	Visit 2 (Randomization)	Treatment Day ≤ 1
Double-Blind Treatment Period	Week 4	Visit 4	Treatment Day [2, 41]
	Week 8	Visit 6	Treatment Day [42, 69]
	Week 12	Visit 7/ET	Treatment Day [70, end of the double-blind treatment period]
Follow-up	Week 16 (Follow-up)	Visit 8	Treatment Day [end of the double-blind treatment period +1, min(end of last study visit, 115)]

ET = early termination. Follow-up visit will not be included in the MMRM analysis and will only be used in summary statistics.

Table 16.1-6. Efficacy Analysis Visit Definitions in the Off-Treatment Hypothetical Estimand Approach for MSQ v2.1 and HIT-6

Analysis Phase	Analysis Visit (Derived)	Window
Pretreatment	Baseline	Treatment Day ≤ 1
On or after the first dose of study intervention	Week 4	Treatment Day [2, 41]
	Week 8	Treatment Day [42, 69]
	Week 12	Treatment Day [70, 97]
	Week 16	Treatment Day [98, end of last study visit]]

ET = early termination. Follow-up visit will not be included in the MMRM analysis and will only be used in summary statistics.

The analysis visit windows for EQ-5D-5L for mITT Population and Off-treatment Hypothetical Estimand Population are defined as follows:

Table 16.1-7. Efficacy Analysis Visit Definitions for EQ-5D-5L

Analysis Phase	Analysis Visit (Derived)	Scheduled Study Visit (eCRF)	Window
Pretreatment	Baseline	Visit 2 (Randomization)	Treatment Day [-7, -1]
Double-Blind Treatment Period	Week 1-2	Visit 3	Treatment Day [1, 14]
	Week 4	Visit 4	Treatment Day [25, 31]
	Week 6	Visit 5	Treatment Day [39, 45]
	Week 8	Visit 6	Treatment Day [53, 59]
	Week 12	Visit 7/ET	Treatment Day [77, minimum(end of the double-blind treatment period, 83)]
Follow-up	Week 16 (Follow-up)	Visit 8	Treatment Day [end of the double-blind treatment period +1, min(end of last study visit, 115)]

ET = early termination. Follow-up visit will not be included in the MMRM analysis and will only be used in summary statistics.

Table 16.1-8. Efficacy Analysis Visit Definitions in the Off-Treatment Hypothetical Estimand Approach for EQ-5D-5L

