End of Double-blind Treatment Period is defined as the last available assessment during double-blind treatment period. End of Double-blind Treatment Period results will be presented in analysis tables for clinical laboratory values and vital signs.

End of Study is defined as the last available assessment during the study, including double-blind and safety follow-up period.

End of Study results will be presented in analysis tables for safety parameters, including but not limited to electrocardiograms, clinical laboratory values, and vital signs.

ET = early termination.

For endpoints collected by visit (not for eDiary data), if a participant has 2 or more visits within the same window, the last visit with a non-missing value will be used for analysis, unless specified otherwise.

The following algorithm is used to define the double-blind treatment period and the follow-up periods unless specified otherwise. The double-blind treatment period starts with the date of the first dose of double-blind study treatment and ends with the latest date of the last study medication date, and the last scheduled assessment date of Visit 2 to Visit 7 for participants who entered the safety follow-up period; or ends with the latest date of the last study medication date, and last assessment date for participants who did not enter the safety follow-up period. The safety follow-up period starts with the 1 day after the end of the double-blind period and ends with the last scheduled assessment date of Visit 8 for participants who entered the estimand follow-up period;

or ends with the last assessment date for participants who did not enter the estimand follow-up period. The estimand follow-up period starts with the 1 day after the end of the safety follow-up period and ends with the last assessment date for participants who entered the estimand follow-up period.

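### EU analysis of HIT-6 and MSQ: SAP 10.3.3 excludes Visit 8 scores by visit name, although an early discontinuer's Visit 8 can fall in the Week 4, 8 or 12 window of Table 16.1-6

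*SAP*

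**What the plan says.** SAP 10.3.3 analyses HIT-6 total score and MSQ v2.1 Role Function-Restrictive with an MMRM like the primary one, focusing on the Week 12 contrast in the Off-treatment Hypothetical Estimand Population. It then adds: "Some participants may have their HIT-6 total score or MSQ v2.1 assessed at Visit 8, which will not be included in MMRM"; those scores are only summarised. SAP 10.2.2 has almost the same sentence for the mITT analysis: "Some participants may have their MSQ v2.1 assessed at Visit 8, which will not be included in MMRM".

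Table 16.1-6 in SAP 16.1 sets the windows for these instruments under the off-treatment estimand. It has no scheduled-visit column. Week 4 is Days 2 to 41, Week 8 is Days 42 to 69, Week 12 is Days 70 to 97, and Week 16 runs from Day 98. Its footnote says: "Follow-up visit will not be included in the MMRM analysis and will only be used in summary statistics". No row of that table is labelled as follow-up. For visit-based endpoints, SAP 16.1 also says that "if a participant has 2 or more visits within the same window, the last visit with a non-missing value will be used for analysis".

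SAP 10.3.1 includes data collected after discontinuation of study drug, unless the participant starts a new preventive. Protocol 7.4.6 applies that approach to the continuous secondary endpoints. Protocol 8.8 places Visit 8 four weeks after the last dose. Under Protocol 8.8.1, if Visit 8 falls at or after Week 12 it is the last visit (Scenario A). If it falls earlier, a Final Study Visit at Day 84 (+7 days) collects both instruments (Scenario B).

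**The concern.** One rule goes by visit name and the other by study day. They agree for completers, whose Visit 8 is near Day 112. They can disagree for anyone who stops treatment early enough for Visit 8 to fall before Day 98. For those participants 10.3.3 discards a score that Table 16.1-6 would place in an MMRM window and that the estimand is meant to use.

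S4 and S5 are alpha-controlled hypotheses in the EU hierarchy (SAP 10.3.3.1). Two programmers, one following 10.3.3 and the other Table 16.1-6, would build different datasets for the same confirmatory test. The literal rule is also uneven. Later discontinuers (Scenario A) lose their off-treatment Week 12 score, while earlier ones (Scenario B) keep theirs through the Final Study Visit.

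**Working it through.** The plan states no figure on this point, so the check is day arithmetic followed by a reading of the texts together.

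**Inputs from the documents.** Visit 8 = last-dose day L + 28 (Protocol 8.8), ± 3 days (Protocol Table 1). Windows are from SAP Table 16.1-6, with the last non-missing score in a window used (SAP 16.1). Scenarios A and B are from Protocol 8.8.1. There are 250 participants per arm.

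**Assumptions.** The early-termination (ET) visit is 0, 3 or 7 days after the last dose. Visits 4 and 6 take place on Days 28 and 56 if the participant is still on treatment. The Final Study Visit is on Day 84. Visit 8 is attended and no new preventive is started.

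**Nominal case (ET on the last-dose day, Visit 8 at L + 28).**

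| Last dose L | Visit 8 day | Window | Effect of dropping the Visit 8 score |
|---|---|---|---|
| 1–13 (13 days) | 29–41 | Week 4 | The earlier ET score is used instead; at L = 1 no Week 4 score remains |
| 14–41 (28 days) | 42–69 | Week 8 | Only Week 8 score lost |
| 42–55 (14 days) | 70–83 | Week 12, Scenario B | None if the Final Study Visit is attended; otherwise only Week 12 score lost |
| 56–69 (14 days) | 84–97 | Week 12, Scenario A | Only Week 12 score lost |
| 70–83 | 98–111 | Week 16 | None |

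Last-dose days with any changed MMRM input, Final Study Visits attended: 13 + 28 + 14 = 55.

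**Range over the nine combinations of ET lag (0, 3, 7) and Visit 8 timing (+25, +28, +31).**

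- Week 12: 14 last-dose days change in every case, and 4 to 14 of them lose the only score. The minimum of 4 arises with ET lag 7 and Visit 8 at +25. There L = 59–72 is affected, but ET reaches Day 70 once L ≥ 63, which leaves L = 59–62.
- Week 8: 28 days change in every case, of which 18 to 28 lose the only score.
- Week 4: 10 to 16 days change.
- Weeks 4 and 8 together: 10 + 28 = 38 to 16 + 28 = 44.
- Any input: 38 + 14 = 52 to 44 + 14 = 58.
- If every Scenario B Final Study Visit were missed: 14 more Week 12 days, all losing the only score.

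**Participants per arm.** Let a proportion d discontinue, evenly over 84 days, with d assumed to be 0.10 to 0.20. The expected number is 250 × d × days / 84.

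- Week 12 value changed: 250 × 0.10 × 14/84 = 4.2 to 250 × 0.20 × 14/84 = 8.3.
- Only Week 12 value lost: 250 × 0.10 × 4/84 = 1.2 to 250 × 0.20 × 14/84 = 8.3.
- Week 4 or Week 8 value changed: 250 × 0.10 × 38/84 = 11.3 to 250 × 0.20 × 44/84 = 26.2.
- Any MMRM input changed: 250 × 0.10 × 52/84 = 15.5 to 250 × 0.20 × 58/84 = 34.5.

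**The texts together.** In the mITT table (16.1-5) the Week 16 row is tied to Visit 8 and begins the day after the double-blind period ends, so excluding Visit 8 and excluding Week 16 amount to the same thing. Table 16.1-6 has no such link. If its footnote means Visit 8, table and text agree, but both conflict with SAP 10.3.1 and Protocol 7.4.6. If it means Week 16, the table conflicts with 10.3.3. Either reading needs an edit.

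**The case against.** The best defence is that the intent is plain. SAP 10.2.3 says, for these same instruments, that "Week 16 (follow up visit) will not be included in MMRM model fitting", and 10.3.4 carries those methods to the EU. The schedule of visits labels Visit 8 as Week 16. The EU additional endpoints include the same scores at other weeks, and one repeated-measures model per instrument would naturally serve both sets, so a score could hardly be in the fit for Weeks 4 and 8 and out of it for Week 12. The 10.3.3 sentence looks carried over from 10.2.2, which would make this a wording slip.

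That is probably what the authors meant. But 10.3.4 covers only the additional endpoints, and the one sentence written for S4 and S5 says something else. The result is two rules for the same scores, and the rule for the confirmatory tests is the one that departs from the estimand.

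Other points stand as limits on size. The Week 4 and Week 8 losses supply most of the any-input count but reach the Week 12 contrast only through the model. The further Scenario B loss needs a required visit to be missed. The discontinuation rate and its even spread have no source in the documents. Withdrawal of consent, loss to follow-up or a new preventive would lower the counts. SAP 10.3.2.1 reports few participants in some on/off-treatment pattern groups, which points to small numbers without giving a rate.

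**Conclusion.** The concern holds. As written, 10.3.3 removes off-treatment HIT-6 and MSQ scores that the EU estimand includes and that Table 16.1-6 would assign to Weeks 4, 8 or 12. The exposure that matters most is Scenario A with Visit 8 on Days 84 to 97. Under the stated assumptions that is about 4 to 8 participants per arm with a changed Week 12 value, including about 1 to 8 with none left. These counts are illustrations, not bounds.

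The effect on the S4 and S5 estimates is probably small, because a participant without a Week 12 score still contributes through earlier scores, and it cannot be computed from the documents. S4 and S5 hold the last two positions in the hierarchy. The primary endpoint, S1 to S3, the mITT analyses, completers, and discontinuers whose Visit 8 falls on Day 98 or later are not affected. It should be fixed because the rule feeds two confirmatory tests and ought not to be left to programming judgement.

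**What to change.** Replace the visit-name exclusion in SAP 10.3.3 and in the footnote to Table 16.1-6 with a window rule, for example: *All HIT-6 and MSQ assessments, including those at Visit 8 or the Final Study Visit, are assigned by study day under Table 16.1-6 and enter the MMRM at Weeks 4, 8 and 12, subject to the rule on new preventive treatment. Only assessments in the Week 16 window (Day 98 onward) are summary-only.* Leave SAP 10.2.2 and 10.4 as they are, since the exclusion fits the mITT analyses. The cost is one sentence and one footnote. No new data are needed, because both instruments are already collected at these visits.
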